APPENDIX C: TOXICITY TABLE

Clinical Adverse Events			
NEUROLOGICAL/ CARDIOVASCULAR	Mild (Grade 1)	Moderate (Grade 2)	Severe (Grade 3)
Pre-syncope/Syncope	Lightheadedness	Dizziness (pre-syncope), diaphoresis and sense of impending doom	Confusion, collapse, loss of consciousness
Hypotension			Decrease in systolic blood pressure greater than 30% from baseline
Pulse		Increase or decrease of 20bpm from baseline	Increase or decrease of 30bpm from baseline
CUTANEOUS	Mild (Grade 1)	Moderate (Grade 2)	Severe (Grade 3)
Urticaria and angioedema	Flushing or sensation of heat or warmth	Generalized urticaria and/or periorbital edema or angioedema (not laryngeal, tongue or uvular)	Generalized urticaria and laryngeal, tongue or uvula swelling with or without stridor
HEENT	Mild (Grade 1)	Moderate (Grade 2)	Severe (Grade 3)
Eyes, face and periorbital area	Conjunctival erythema, pruritus or tearing	Conjunctivitis plus rhinitis (e.g., sneezing, rhinorrhea, nasal pruritus and/or nasal congestion),	
Upper respiratory		Cough perceived to come from the upper airway (not the lungs, larynx, or trachea) without stridor	Upper respiratory symptoms and cough perceived to come from the lungs, larynx, or trachea with stridor
RESPIRATORY	Mild (Grade 1)	Moderate (Grade 2)	Severe (Grade 3)

Shortness of breath (bronchospasm)	Transient; no treatment; 71% - 80% of baseline peak flow	Bronchospasm (dyspnea, hoarseness, wheeze) that requires medical intervention; normalizes with bronchodilator; 60% - 70% (of baseline peak flow)	<60% of baseline peak flow Bronchospasm that does not resolve or progresses to respiratory failure
GASTROINTESTINAL	Mild (Grade 1)	Moderate (Grade 2)	Severe (Grade 3)
Abdominal cramps, vomiting or diarrhea	Transient abdominal cramps	Abdominal cramps, nausea, vomiting or diarrhea	Abdominal cramps, nausea, vomiting or diarrhea with signs/symptoms of dehydration that requires medical intervention

APPENDIX D: PROVIDER FEASIBILITY SURVEY

SECTION 1: PRE-TRIAL SURVEY

1. What is your practice setting? **Check (X) only one**

- a. Public health clinic |
- b. Outpatient primary care clinic |
- c. Outpatient specialty clinic ► **Specify** |
- d. Other clinic setting ► **Specify**: |

2. What type of provider are you? **Check (X) only one**

- a. Physician (MD/DO) |
- b. Nurse practitioner |
- c. Physician assistant |
- d. RN |
- e. Other ► **Specify**: |

3. What is your specialty or defined area of practice? **Check (X) all that apply**

- a. Adult medicine |
- b. Family medicine |
- c. Infectious disease only |
- d. Pediatric/Adolescent medicine |
- e. OB-GYN |
- f. Preventive medicine |
- g. Other ► **Specify**: |

4. What is your current approach to penicillin (PCN) allergic patients? **Check (X) all that apply**

- a. Use alternative antibiotic |
- b. Penicillin skin testing |
- c. Oral challenge |
- d. Referral to allergist |
- e. Other ► **Specify**: |

5. Do you have access to PCN skin testing? .. |

0=No (**Skip to Q8**)

1=Yes (Continue to Q6)

6. Do you offer/perform PCN skin testing on site?|____|

0=No

1=Yes

7. What are the barriers to offering / performing PCN skin test to your allergic patients?

Check (X) all that apply

- a. Lack of training|____|
- b. Cost of testing|____|
- c. Length of time to perform test|____|
- d. Fear of precipitating a severe allergic reaction in a patient|____|
- e. I don't think PCN skin testing is necessary|____|
- f. Not interested in offering / performing skin testing|____|
- g. Other ► **Specify:** _____ |____|

8. Do you have offer / perform oral challenge for your PCN allergic patients?|____|

0=No (**Skip to Q10**)

1=Yes (**Continue to Q9**)

9. Who do you test? **Check (X) all that apply**

- a. Patients with low risk history and skip skin testing|____|
- b. Patients who are negative on skin test|____|
- c. Other criteria used ► **Specify:** _____ |____|

10. What are the barriers to offering / performing oral challenge to your PCN allergic patients?

Check (X) all that apply

- a. Lack of training|____|
- b. Cost of testing|____|
- c. Length of time to perform test|____|
- d. Fear of precipitating a severe allergic reaction in a patient|____|
- e. I don't think oral challenge is necessary|____|
- f. Not interested in offering / performing an oral challenge|____|
- g. Other ► **Specify:** _____ |____|

SECTION 2: POST-TRIAL SURVEY

1. What is your practice setting? **Check (X) only one**
 - a. Public health clinic
 - b. Outpatient primary care clinic
 - c. Outpatient specialty clinic ► **Specify** _____
 - d. Other clinic setting ► **Specify**: _____

2. What type of provider are you? **Check (X) only one**
 - a. Physician (MD/DO)
 - b. Nurse practitioner
 - c. Physician assistant
 - d. RN
 - e. Other ► **Specify**: _____

3. What is your specialty or defined area of practice? **Check (X) all that apply**
 - a. Adult medicine
 - b. Family medicine
 - c. Infectious disease only
 - d. Pediatric/Adolescent medicine
 - e. OB-GYN
 - f. Preventive medicine
 - g. Other ► **Specify**: _____

4. What is your current approach to penicillin (PCN) allergic patients? **Check (X) all that apply**
 - a. Use alternative antibiotic
 - b. Penicillin skin testing
 - c. Oral challenge
 - d. Referral to allergist
 - e. Other ► **Specify**: _____

5. Prior to the trial, did you offer/perform PCN skin testing on site?
0=No
1=Yes

6. Prior to the trial, did you offer/perform oral challenge for your PCN allergic patients? |____|

0=No

1=Yes

7. Which PCN allergy intervention did you perform? |____|

0=PCN Skin Testing

1=Direct Oral Challenge

2=Both

8. Which method did you prefer? |____|

0=PCN Skin Testing

1=Direct Oral Challenge

2=No preference

9. Please explain why you preferred the allergy intervention method you chose in Q8.

Describe: _____

10. After participating in the trial, do you feel PCN allergy assessment can be performed safely and effectively in a setting which treats patients with STIs? **Check (X) only one**

a. Strongly agree |____|

b. Somewhat agree |____|

c. Neither agree nor disagree |____|

d. Somewhat disagree |____|

e. Strongly disagree |____|

11. Do you think your clinic will offer this service in the future? |____|

0=No ► **Continue to Q7**

1=Yes ► **End of survey. Skip to initials**

12. Please indicate the reasons you will not offer PCN allergy assessment in the future. **Check (X) all that apply**

a. Lack of organizational support |____|

b. Reimbursement |____|

c. Local site training |____|

- d. Don't believe that the results will be useful|__|
- e. Risk of adverse reaction|__|
- f. Lack of time for providers to do the testing|__|
- g. Lack of access to reagents|__|
- h. Other barriers to offering / performing this service ► **Describe:** _____
.....|__|

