5.4 Provider Feasibility Sub Study Population

At each site, we will conduct a short feasibility Sub Study among the clinicians to determine the practicality of performing PCN (B-lactam) skin testing and oral challenge in the ambulatory STD setting (see secondary objective). Since this is an operational feasibility assessment, the sampled population will be clinicians who evaluate and treat patients at the participating clinic sites. The surveys will be administered once at the beginning of the study and again at the end. We estimate that there will be 15-30 eligible clinicians per site over the course of the study. Accounting for personnel turnover, we anticipate that the total sample will be no more than 150 individual respondents.

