6.2 PCN Skin Testing

Depending on the outcome of the PCN (B-lactam) allergy history screening questionnaire, participants may qualify to receive the PCN skin test.

- Participants with a higher risk of PCN allergy will not proceed to the PCN skin test or oral challenge. Their study participation will be complete. Subjects will be provided with a written referral to local allergy providers.
- Participants with a low risk of PCN allergy and assigned to the PST intervention group will be offered the PCN skin test.

Staff will verify that qualified participants do not meet any additional criteria that would preclude them from skin testing using the Skin Test Qualification Checklist. Study staff will explain the skin testing procedures to participants who may decide to accept or decline skin testing. If they decline, they will be asked to complete the subject acceptability survey and their study participation will be complete. Staff will note the reason(s) they declined to be skin tested on the appropriate CRF.

Study staff will perform the allergy skin testing for PCN allergy in accordance with standard allergy testing procedures and instructions provided in the PRE-PEN® kit package insert.³¹ Prick (Puncture) tests will be performed before proceeding to intradermal testing. Prick testing is performed at marked sites on the inner volar aspect of the forearm. Testing for controls and each reagent is performed singly.

Reagents and controls for prick and intradermal tests include:

1. Controls:
 - a.) Negative Control: Sodium chloride solution without preservative

* e.g., patients presenting with secondary syphilis

- b.) Positive Control: Histamine:
 - i. Prick testing: histamine base 1 mg/ml
 - ii. Intradermal testing: histamine base 0.1 mg/ml
2. Reagents:
 - a.) PRE-PEN® (major determinant)
 - b.) Penicillin G 10,000 U/ml (minor determinant)

Intradermal testing will not be performed if there is a positive or uninterpretable reaction to PRE-PEN® and/or Penicillin G during the prick test. If the prick skin test results are negative the participant is qualified for intradermal testing. Study staff will perform duplicate intradermal skin testing of each reagent and single intradermal skin testing of the positive and negative controls on the inner volar aspect of the forearm. The same arm will be used for both prick and intradermal testing.

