8.1.2 Secondary Outcome Measures

The following secondary outcome measures will be used to address the secondary study objectives:

- Acceptability
 - Proportion of study subjects who find the testing procedures to be helpful.
 - Reasons why study subjects refuse to participate in the study or find the testing procedures to be of no value.
 - Proportion of study subjects who were negative on oral challenge who now feel confident in taking PCN or similar antibiotics.
 - Proportion of study providers who will not offer PCN allergy assessment in the future.
- Feasibility
 - Proportion of study providers who will offer PCN allergy assessment in the future.
 - Reasons why study providers will not offer PCN allergy assessment in the future.
- Both acceptability and feasibility
 - Types and frequencies of elicited reactivity to PCN through skin testing and oral challenge among study subjects.

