3.2 Secondary Outcome measures

- Acceptability
 - Proportion of study subjects who find the testing procedures to be helpful.
 - Reasons why study subjects refuse to participate in the study.
 - Proportion of study subjects who were negative on oral challenge who now feel confident in taking PCN or similar antibiotics.
 - Proportion of study providers who will not offer PCN allergy assessment in the future.
- Feasibility
 - Proportion of study providers who will offer PCN allergy assessment in the future.
 - Reasons why study providers will not offer PCN allergy assessment in the future.
- Both acceptability and feasibility
 - Types and frequencies of elicited reactivity to PCN through skin testing and oral challenge among study subjects.

4. Analysis Populations

This analysis plan describes six different analysis populations that are used for different purposes. The final statistical report will include an accounting of all eligible persons screened and the number enrolled. The reason for excluding any data from any analysis population will be documented.

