7.4 Analysis of Secondary Objective

For the following measures, the frequencies and the percentages with corresponding exact 95% confidence intervals of participants will be tabulated by intervention group (if available), , study site and overall in the following measures.

7.4.1 Assessment of Subject Acceptability/Feasibility:

In the Eligible Population:

- those who refuse to participate in the study. The reasons of not interested in participating in the study will be summarized.

- For those who prefer to see an allergist for skin testing, summarize the reasons why they have not seen an allergist until now.

In the Treated Population:

- those who experience elicited reactivity to PCN allergy skin testing in the PST Group and oral challenge by dosage and group.
- those who find the testing procedures of to be helpful. The reasons of finding the PCN testing not helpful will be summarized.
- Those feeling comfortable with allergy testing conducted in settings where STD services are provided rather than by an allergist.
- chance of referring a friend or family member having a history of penicillin allergy.
- confidence in taking PCN or similar antibiotics among those who have been skin tested and are negative for PCN allergy.

7.4.2 Assessment of Provider Acceptability/Feasibility:

In the Provider Population, summarize by group (if possible) in numbers and proportion of:

- those who prefer PCN skin testing, direct oral challenge, or no preference.
- those who feel PCN allergy assessment can be performed safely and effectively in a setting which treats patients with STIs.
- those who will offer PCN allergy assessment in the future.
- reasons why study providers will not offer PCN allergy assessment in the future.

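### The post-trial provider survey asks whether the clinic, not the provider, will offer allergy assessment, misroutes 'No' answers, and has no place for clinicians who performed neither method

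*Protocol*

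**What the plan says.** Protocol 3.2.2 and 8.1.2 and SAP 3.2 define the outcome at the level of the provider. Under feasibility it is "Proportion of study providers who will offer PCN allergy assessment in the future". Under acceptability it is the complement: "Proportion of study providers who will not offer PCN allergy assessment in the future". SAP 7.4.2 repeats the first as a measure in the Provider Population. Protocol 8.4.2 extends to providers the exact 95% intervals used for participants, and SAP 7.4 plans exact intervals by study site and overall.

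The post-trial survey (protocol Appendix D, Section 2) has one item on future offering, Q11: "Do you think your clinic will offer this service in the future". 'Yes' ends the survey and 'No' sends the respondent to Q7. Q12 then reads: "Please indicate the reasons you will not offer PCN allergy assessment in the future".

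Q7 asks "Which PCN allergy intervention did you perform" and accepts skin testing, direct oral challenge or both. Q8 asks every respondent which method they preferred, and Q9 asks why. Protocol 5.4 says who is surveyed: "the sampled population will be clinicians who evaluate and treat patients at the participating clinic sites". Protocol 6.2 says who tests: "Study staff will perform the allergy skin testing for PCN allergy in accordance with standard allergy testing procedures". SAP 4.6 counts every provider who completes the survey, and SAP 7.4.2 tabulates in that population "those who prefer PCN skin testing, direct oral challenge, or no preference".

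**The concern.** A provider and a clinic can give different answers. A nurse who would gladly test, in a clinic without reagents or organizational backing, is counted as a provider who will not offer assessment. A reluctant clinician in a clinic that has decided to go ahead is counted as one who will. The report would carry a provider-intention label on a figure that is a forecast of clinic adoption, and it would do so twice, because the acceptability outcome is the same item reversed.

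The method-preference table has a related weakness. It may pool clinicians who used the methods with clinicians who only worked in the same building. Neither gap can be repaired from the data once the survey closes.

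**Working it through.** **1. Unit of each item, side by side.**

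| Place | Whose action |
|---|---|
| Protocol 8.1.2, SAP 3.2 and 7.4.2: will / will not offer | provider |
| Post-trial Q5 and Q6: past offering | provider |
| Post-trial Q11: future offering | clinic |
| Post-trial Q12: reasons for not offering | provider |

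No post-trial item asks whether the respondent personally will offer assessment. The unit moves from person to clinic at Q11 and back to person at Q12.

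**2. Skip logic.** 'Yes' at Q11 ends the survey. 'No' goes back to Q7. As printed, neither answer leads to Q12, the only source for the listed outcome on providers' reasons.

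**3. Number of respondents.** Protocol 5.4 gives 15–30 eligible clinicians per site and a ceiling of 150; protocol 6.5 speaks of five clinics. 5 × 30 = 150 reproduces the ceiling. The four sites of the Protocol Summary would give 4 × 30 = 120, which does not. Protocol 6.5 expects 50–100 surveys from staff present at both start and end, which I read as 50/5 = 10 to 100/5 = 20 respondents per clinic. The 15–30 count runs over the whole study, so 30 per clinic is an upper limit, not the expected post-trial number.

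**4. Interval if respondents were independent.** The exact limits are the 0.025 quantile of Beta(x, n−x+1) and the 0.975 quantile of Beta(x+1, n−x). With 60% 'Yes' (an assumption):

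| n | Exact 95% CI |
|---|---|
| 50 | 45.2–73.6% |
| 100 | 49.7–69.7% |
| 150 | 51.7–67.9% |

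**5. Effect of clustering.** With m respondents in each of five clinics, the design effect is 1 + (m−1) × ICC and the effective n is 5m divided by it. The ICC (intraclass correlation) is not in the documents, so a range is shown.

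| ICC (assumed) | m = 10, n = 50 | m = 30, n = 150 |
|---|---|---|
| 0.1 | 50/1.9 = 26.3 | 150/3.9 = 38.5 |
| 0.3 | 50/3.7 = 13.5 | 150/9.7 = 15.5 |
| 0.5 | 50/5.5 = 9.1 | 150/15.5 = 9.7 |
| 1 | 50/10 = 5 | 150/30 = 5 |

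At any ICC above zero the independent-binomial interval is too narrow. By how much depends on a quantity nobody has yet.

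**6. Preference.** A clinician who performed neither method has no valid code at Q7 and is still asked Q8. As an illustration, suppose those with experience split 60% direct challenge, 25% skin testing and 15% no preference, and that all others tick 'No preference'. If a share f performed neither, the reported direct-challenge figure is 60% × (1−f): 45%, 30% and 15% for f = 25%, 50% and 75%. 'No preference' becomes 15% × (1−f) + f: about 36%, 58% and 79%. Under this assumption the ratio of the two methods stays at 60:25; if the others guess instead, the ratio can shift as well.

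**The case against.** Q11 can be defended. The secondary objective is feasibility in an ambulatory setting, protocol 5.4 calls the sub study operational, and several Q12 reasons (organizational support, reimbursement, reagents) lie with the clinic. Q11 also asks what the respondent thinks, so it records an individual's view. This stands as a reason to keep the clinic item. It does not make that item a measure of what the provider will do, which is what both documents list.

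SAP 7.4 already tabulates by site, so differences between clinics would be visible. That stands too, but the overall interval is still planned. Q11 is not the only provider proportion either: SAP 7.4.2 also reports Q10 (whether assessment can be done safely and effectively) and method preference. And the figures are descriptive, with no test, power claim or decision rule resting on them.

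Three stronger readings are tempting and not supported:

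- A reader might infer that the interval should be as wide as 3 clinics of 5 would give (14.7–94.7%). That needs complete agreement within every clinic, and nothing in the documents supports it.
- A reader might infer that Q7 forces false answers. Nothing says Q7 is mandatory, SAP section 5 provides for missing data, and Q8 offers 'No preference'. That some respondents performed neither method is itself an inference: study staff do the testing, but no passage says clinic clinicians cannot be study staff.
- A reader might infer that all provider outcomes are mismeasured. Method preference is a SAP measure, not a listed outcome, and the wording of Q12 does match the listed outcome on reasons.

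**Conclusion.** The point holds for what Q11 measures. A listed secondary outcome and its complement rest on an item about the clinic, so the reported proportion will be expected clinic adoption. The broken skip to Q12 is a plain error in the printed form. These two findings come from the text and need no assumption.

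The interval point holds only in direction: clustering by clinic is likely, and the exact interval may be too narrow by an amount that cannot be stated. The effective sample sizes above rest on assumed ICCs, equal clinic sizes and a 60% split.

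The Q7–Q8 point holds as a possibility. Respondents are not required to have performed study testing and the form has no code for those who did not, but their share is unknown. None of this touches the primary outcomes. It is worth correcting because the correction is cheap and the missing answers cannot be recovered later.

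**What to change.** - Add a provider-level item to the post-trial survey, for example: Will you offer or perform PCN allergy assessment in the future? Name it in SAP 3.2 and 7.4.2 as the source of the will / will not offer outcomes.
- Keep Q11 as a separate clinic item, label it as expected clinic adoption, and report it by site.
- Route 'No' on the new item to Q12, and remove the skip from Q11 to Q7.
- Add 'Neither' to Q7.
- In SAP 7.4.2, report method preference by Q7 answer, with those who performed both methods as the main comparison and the others shown separately.
- Note beside any overall provider interval that it ignores clustering by clinic. Asking about the provider instead of the clinic does not remove that clustering.

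The cost is one more item on a short electronic survey, a few SAP lines, and a smaller denominator for preference.

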7.2 Analysis of Baseline Data

Baseline variables will be summarized for the Treated population, the Enrolled population and the Per Protocol Population. The following baseline measures collected at the screening and enrolment visits from participants will be summarized by treatment group:

- Demographic data: age, gender, ethnicity and race.
- Allergy history
- Vital signs and focused physical exam

For PST Group only:

- HIV status, last CD4 (within last 6 months) and HAART status if HIV+
- Skin conditions
- Skin testing history

For DOC Group only:

- Current pregnancy status of female participants (assigned female at birth)

The following pre-trial survey results of providers will be summarized by site:

- Practice setting
- Type of provider
- Specialty or defined area of practice

- Current approach to penicillin (PCN) allergic patients
- Access to PCN skin testing and whether PCN skin testing/oral challenge is offered.
- Barriers to offering/performing PCN skin test/oral challenge

Data will be presented in summary tables by treatment group, site and overall. Categorical variables, and continuous variables that have been categorized at discrete levels, will be summarized by frequencies and percentages. Continuous variables will be summarized in means, standard deviations, medians, minima and maxima.

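### As printed, the post-trial provider survey sends a No at Q11 to Q7 instead of Q12, so the item that collects a listed secondary outcome cannot be reached

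*Protocol*

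**What the plan says.** The Protocol lists "Reasons why study providers will not offer PCN allergy assessment in the future" as a feasibility outcome (Sections 3.2.2 and 8.1.2) and plans its analysis in Section 8.4.2. The SAP lists the same outcome in Section 3.2, and Section 7.4.2 summarises "reasons why study providers will not offer PCN allergy assessment in the future" in the Provider Population.

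The instrument is in Protocol Appendix D, Section 2. The relevant items are:

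- Q7: "Which PCN allergy intervention did you perform"
- Q11: whether the clinic will offer the service in future. No is marked "Continue to Q7"; Yes is marked "End of survey. Skip to initials".
- Q12: "Please indicate the reasons you will not offer PCN allergy assessment in the future", with a check-all list of reasons.

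Protocol Section 6.5 has providers complete the survey themselves as an electronic form. Section 6.6.1 says these data are collected on iPads, in a data system that is to be validated before use.

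**The concern.** Q12 applies only to providers who answer No at Q11, and the printed instruction sends exactly those providers somewhere else. A reader with a paper form would probably carry on to the next item. An electronic form that follows the printed specification need not allow that.

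Nothing else in the post-trial survey replaces Q12. Q9 asks why one testing method was preferred over the other. Q10 asks for agreement that assessment can be done safely and effectively. Neither asks why the service will not be offered. The pre-trial barrier items cannot stand in for it either, because they are answered before the provider has taken part in the trial.

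The proportions of providers who will or will not offer assessment come from Q11 itself. What is at stake is therefore the reasons outcome.

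**Working it through.** No sample size, power or error rate is involved, and the plan gives no figure to reproduce. The check is to follow the printed instructions and list which items a respondent can reach.

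**Inputs** (Appendix D, Section 2): Q1 to Q10 carry no skips, so each leads to the next. Q11 No leads to Q7. Q11 Yes leads to the end.

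**Post-trial survey as printed**

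| Answer at Q11 | Route from Q11 | Q12 reached? |
|---|---|---|
| Yes | end of survey | no |
| No | Q7, Q8, Q9, Q10, Q11, and round again | no |

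The reachable set is Q1 to Q11. Q12 has no route into it.

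**Post-trial survey with Q11 No leading to Q12**

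The reachable set is Q1 to Q12, and Q12 is asked of exactly those who answer No.

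**How many providers this concerns**

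Protocol Section 6.5 expects 50 to 100 surveys from staff present at both the beginning and the end. The documents give no expected share of No at Q11, so I assume a range of 10% to 50%.

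| Assumed share of No | 50 providers | 100 providers |
|---|---|---|
| 10% | 0.10 × 50 = 5 | 0.10 × 100 = 10 |
| 50% | 0.50 × 50 = 25 | 0.50 × 100 = 50 |

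About 5 to 50 providers' reasons would depend on the Q11 instruction. Staff who joined during the study and completed only the closing survey would add to this; the documents do not give their number.

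**Pre-trial survey, for comparison** (Appendix D, Section 1)

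Q5 (access to skin testing) sends No to Q8 and Yes to Q6. Q6 (offers or performs skin testing on site) has no skip, so either answer leads to Q7, "What are the barriers to offering / performing PCN skin test to your allergic patients". Q8 (offers or performs oral challenge) sends No to Q10, the oral challenge barriers, and Yes to Q9 and then Q10. This gives four routes:

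| Q5 | Q8 | Skin-test barriers (Q7) | Oral challenge barriers (Q10) |
|---|---|---|---|
| No | No | not asked | asked |
| No | Yes | not asked | asked |
| Yes | No | asked | asked |
| Yes | Yes | asked | asked |

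Every pre-trial item can be reached and every skip leads forward. Only the post-trial Q11 instruction points backward and leaves an item stranded.

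**The case against.** The strongest reply is that this is a wrong number with an obvious intention. In the pre-trial survey, an instruction to continue always names the next item (Q5 Yes to Q6, Q8 Yes to Q9), and jumps are labelled as skips. By that convention Q11 No continues to Q12. The wording of Q12 fits only providers who said No, and the SAP plans to summarise its answers. A form built literally would trap every No respondent in a loop, which testing should expose, and Protocol Section 6.6.1 requires the system to be validated against the study's scientific and logistical requirements before use.

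This stands as far as it goes: the intention is clear, and the documents do not show that any data were or will be lost. It does not make the printed rule correct. The rule is an operating instruction in a self-administered electronic form, and the documents do not show the programmed logic.

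A reader might also infer that the pre-trial Q5 skip is a second misroute, because providers without access never see Q7 whereas a No at Q8 does lead to the oral challenge barriers. The documents do not support that. The counterpart of Q8 is Q6, since both ask whether the provider offers or performs the test, and Q6 No does lead to Q7. Q5 is a separate gate on access with no oral challenge counterpart, and a No there already records the lack of access. Providers who have access but do not test are still asked about barriers. The SAP uses these answers only as descriptive baseline data by site ("Barriers to offering/performing PCN skin test/oral challenge", Section 7.2), not as a secondary outcome, and plans no comparison between the two sets of barriers.

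Nor can the number without access be put at most of 150 providers. Protocol Section 2.1 describes testing in most busy settings as either unavailable or hard to obtain, and a provider with difficult access may still answer Yes. The 150 is a ceiling on all individual respondents over the study, after turnover, and is not a count of pre-trial surveys.

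**Conclusion.** The point holds for post-trial Q11. As printed, Q12 is unreachable, and with it the only direct source for a secondary outcome named in both documents. The inference that the reasons will not be collected goes further than the documents allow. Loss depends on the form having been built literally from Appendix D, which cannot be judged from what is provided.

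If it was built that way, all the reasons would be missing. That is about 5 to 50 providers, under the assumed 10% to 50% share of No and the 50 to 100 paired surveys. The matter is confined to the provider sub-study. Neither primary outcome nor any participant data is affected.

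The pre-trial Q5 skip is not an error. Its only consequence is that the skin-test barrier summary describes providers with access to skin testing.

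**What to change.** - In Appendix D, Section 2, change the target of Q11 No from Q7 to Q12.
- Verify the skip logic in the built form by testing both answers at Q11, and keep a record of the test.
- If surveys are already complete, establish whether Q12 was displayed to those who answered No. Report how many answered No, how many of them gave reasons and how many have reasons missing.
- Optionally, label the skin-test barrier summary under SAP Section 7.2 as covering providers with access to skin testing only. No change to the Q5 routing is needed.

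The cost is one number in the appendix, a short check of the form and, at most, a table footnote. Design, sample size and the planned analyses stay as they are.
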